7.2.5. Physical Examination

A full physical examination or symptom-directed physical examination will be performed at the timepoints specified in the Schedule of Assessments in Appendix 8.

8. SAMPLE SIZE AND DATA ANALYSIS

8.1. Determination of Sample Size

Approximately 14 subjects will be enrolled in order that approximately 12 subjects complete the study. The sample size for this study was based upon precedent set by other PK studies of a similar nature and was not based on power calculations.

8.2. Analysis Populations

8.2.1. Pharmacokinetic Population

The PK population will include all subjects who received at least 1 dose of sotorasib and have evaluable PK data. The PK population for the primary endpoint analysis will include all subjects who received both sotorasib, and sotorasib in combination with omeprazole and an acidic

18 May 2022 Page 35 of 69

beverage, and have evaluable PK data. A subject will be excluded from the PK summary statistics and statistical analysis if the subject has an adverse event of vomiting that occurs at or before 2 times median t_{max} or diarrhea within 24 hours of dosing.

8.2.2. Safety Population

The safety population will include all subjects who received at least 1 dose of sotorasib and have at least 1 postdose safety assessment.

8.3. Pharmacokinetic Analyses

The plasma PK parameters of sotorasib on Days 1 and 9 will be calculated using standard noncompartmental methods.

The primary PK parameters are C_{max} , AUC_{inf} , and AUC_{last} for sotorasib. A linear mixed-effects model will be used to analyze log-transformed primary PK parameters. The model will assume fixed effect for treatment and a random effect for subject. Geometric mean ratios for C_{max} and AUC values and associated 90% confidence intervals (Test/Reference) will be estimated. The "Reference" treatment for PK analysis will be sotorasib administered alone with water, while the "Test" treatment will be omeprazole administered in combination with sotorasib and an acidic beverage.

Additional parameters may be calculated. Specific details will be presented in the Statistical Analysis Plan for this study.

8.4. Safety Analysis

The number and percentage of subjects reporting any adverse events will be tabulated by Medical Dictionary for Regulatory Activities system organ class and preferred term. Tables of fatal adverse events, serious adverse events, adverse events leading to withdrawal from investigational product or other protocol-required therapies, and significant treatment-emergent adverse events will also be provided. Subject-level data may be provided instead of tables if the subject incidence is low.

Endpoints for clinical laboratory tests, ECG, and vital signs will be summarized.

8.5. Interim Analysis

No interim analyses are planned for this study.

10. APPENDICES

18 May 2022 Page 39 of 69

Appendix 1: Safety Events: Definitions and Procedures for Recording, Evaluating, Follow-up, and Reporting of Adverse Events and Serious Adverse Events

Definition of Adverse Event

Adverse Event Definition

- An adverse event is any untoward medical occurrence in a clinical study subject irrespective of a causal relationship with the study treatment.
- Note: An adverse event can therefore be any unfavorable and unintended sign (including an abnormal laboratory finding), symptom, or disease (new or exacerbated) temporally associated with the use of a treatment, combination product, medical device, or procedure.
- Note: Treatment-emergent adverse events will be defined in the Statistical Analysis Plan.

Events Meeting the Adverse Event Definition

- Any abnormal laboratory test results (hematology, clinical chemistry, or urinalysis)
 or other safety assessments (eg, electrocardiogram, radiological scans, vital signs
 measurements), including those that worsen from baseline, that are considered
 clinically significant in the medical and scientific judgment of the Investigator (ie,
 not related to progression of underlying disease).
- Exacerbation of a chronic or intermittent pre-existing condition including either an increase in frequency and/or intensity of the condition.
- New conditions detected or diagnosed after study treatment administration even though it may have been present before the start of the study.
- Signs, symptoms, or the clinical sequelae of a suspected drug-drug interaction.
- Signs, symptoms, or the clinical sequelae of a suspected overdose of either study treatment or a concomitant medication. Overdose per se will not be reported as an adverse event/serious adverse event unless it is an intentional overdose taken with possible suicidal/self-harming intent. Such overdoses are to be reported regardless of sequelae.
- "Lack of efficacy" or "failure of expected pharmacological action" per se will not be reported as an adverse event or serious adverse event. Such instances will be captured in the efficacy assessments. However, the signs, symptoms, and/or clinical sequelae resulting from lack of efficacy will be reported as adverse events or serious adverse events if they fulfill the definition of an adverse event or serious adverse event.

18 May 2022 Page 40 of 69

Events NOT Meeting the Adverse Event Definition

- Medical or surgical procedure (eg, endoscopy, appendectomy): the condition that leads to the procedure is the AE.
- Situations in which an untoward medical occurrence did not occur (social and/or convenience admission to a hospital).
- Anticipated day-to-day fluctuations of pre-existing disease(s) or condition(s) present or detected at the start of the study that do not worsen.

Definition of Serious Adverse Event

A Serious Adverse Event is defined as any untoward medical occurrence that meets at least 1 of the following serious criteria:

Results in death (fatal)

Immediately life-threatening

The term "life-threatening" in the definition of "serious" refers to an event in which the subject was at risk of death at the time of the event. It does not refer to an event, which hypothetically might have caused death, if it were more severe. For instance, drug-induced hepatitis that resolved without evidence of hepatic failure would not be considered life threatening even though drug-induced hepatitis can be fatal.

Requires in-patient hospitalization or prolongation of existing hospitalization

In general, hospitalization signifies that the subject has been detained (usually involving at least an overnight stay) at the hospital or emergency ward for observation and/or treatment that would not have been appropriate in the physician's office or outpatient setting. Complications that occur during hospitalization are an adverse event. If a complication prolongs hospitalization or fulfills any other serious criteria, the event is serious. When in doubt as to whether "hospitalization" occurred or was necessary, the adverse event is to be considered serious. Hospitalization for elective treatment of a pre-existing condition that did not worsen from baseline is not considered an adverse event.

Results in persistent or significant disability/incapacity

The term "disability" means a substantial disruption of a person's ability to conduct normal life functions. This definition is not intended to include experiences of relatively minor medical significance such as uncomplicated headache, nausea, vomiting, diarrhea, influenza, and accidental trauma (eg, sprained ankle) which may interfere with or prevent everyday life functions but do not constitute a substantial disruption.

18 May 2022 Page 41 of 69

Is a congenital anomaly/birth defect

Other medically important serious event

Medical or scientific judgment is to be exercised in deciding whether serious adverse event reporting is appropriate in other situations such as important medical events that may not be immediately life-threatening or result in death or hospitalization but may jeopardize the subject or may require medical or surgical intervention to prevent 1 of the other outcomes listed in the above definition. These events are typically to be considered serious.

Examples of such events include invasive or malignant cancers, intensive treatment in an emergency room or at home for allergic bronchospasm, blood dyscrasias or convulsions that do not result in hospitalization, or development of drug dependency or drug abuse.

Recording Adverse Events and Serious Adverse Events

Adverse Event and Serious Adverse Event Recording

- When an adverse event or serious adverse event occurs, it is the responsibility of the Investigator to review all documentation (eg, hospital progress notes, laboratory, and diagnostics reports) related to the event.
- The Investigator will then record all relevant adverse event/serious adverse event information in the Event electronic Case Report Form (eCRF).
- The Investigator must assign the following adverse event attributes:
 - Adverse event diagnosis or syndrome(s), if known (if not known, signs or symptoms);
 - o Dates of onset and resolution (if resolved);
 - O Did the event start prior to first dose of investigational product;
 - Assessment of seriousness;
 - Severity (or toxicity defined below);
 - Assessment of relatedness to the investigational product(s) and/or studymandated procedures;
 - o Action taken; and
 - Outcome of event.
- If the severity of an adverse event changes from the date of onset to the date of resolution, record as a single event with the worst severity on the appropriate eCRF.

18 May 2022 Page 42 of 69

- It is not acceptable for the Investigator to send photocopies of the subject's medical records to the Sponsor in lieu of completion of the appropriate eCRF page.
- If specifically requested, the Investigator may need to provide additional follow-up information, such as discharge summaries, medical records, or extracts from the medical records. In this case, all subject identifiers, with the exception of the subject number, will be blinded on the copies of the medical records before submission to the Sponsor.
- The Investigator will attempt to establish a diagnosis of the event based on signs, symptoms, and/or other clinical information. In such cases, the diagnosis (not the individual signs/symptoms) will be documented as the adverse event/serious adverse event.

Evaluating Adverse Events and Serious Adverse Events

Assessment of Severity

The Investigator will make an assessment of severity for each adverse event and serious adverse event reported during the study. The assessment of severity will be based on the Common Terminology Criteria for Adverse Events (CTCAE) grading scale. For the CTCAE grading scale version 5.0, refer to: http://ctep.cancer.gov/protocolDevelopment/electronic applications/ctc.htm.

Assessment of Causality

- The Investigator is obligated to assess the relationship between investigational product(s), protocol-required therapy, and/or study-mandated procedure and each occurrence of each adverse event/serious adverse event.
- Relatedness means that there are facts or reasons to support a relationship between investigational product and the event.
- The Investigator will use clinical judgment to determine the relationship.
- Alternative causes, such as underlying disease(s), concomitant therapy, and other risk factors, as well as the temporal relationship of the event to study treatment administration will be considered and investigated.
- The Investigator will also consult the Investigator's Brochure and/or Product Information, for marketed products, in his/her assessment.
- For each adverse event/serious adverse event, the Investigator must document in the medical notes that he/she has reviewed the adverse event/serious adverse event and has provided an assessment of causality.
- There may be situations in which a serious adverse event has occurred and the Investigator has minimal information to include in the initial report. However, it is

18 May 2022 Page 43 of 69

- very important that the Investigator always make an assessment of causality for every event before the initial transmission of the serious adverse event data.
- The Investigator may change his/her opinion of causality in light of follow-up information and send a serious adverse event follow-up report with the updated causality assessment.
- The causality assessment is 1 of the criteria used when determining regulatory reporting requirements.

Follow-up of Adverse Event and Serious Adverse Event

- The Investigator is obligated to perform or arrange for the conduct of supplemental measurements and/or evaluations as medically indicated or as requested by the Sponsor to elucidate the nature and/or causality of the adverse event or serious adverse event as fully as possible. This may include additional laboratory tests or investigations, histopathological examinations, or consultation with other health care professionals.
- If a subject is permanently withdrawn from protocol-required therapies because of a serious adverse event, this information must be submitted to the Sponsor.
- If a subject dies during participation in the study or during a recognized follow-up period, the Investigator will provide the Sponsor with a copy of any postmortem findings including histopathology.
- New or updated information will be recorded in the originally completed eCRF.
- The Investigator will submit any updated serious adverse event data to the Sponsor within 24 hours of receipt of the information.

Reporting of Serious Adverse Event

Serious Adverse Event Reporting via Paper Serious Adverse Event Report Form

- Facsimile transmission of the Serious Adverse Event Report Form (see Figure 2) is the preferred method to transmit this information.
- In rare circumstances and in the absence of facsimile equipment, notification by telephone is acceptable with a copy of the Serious Adverse Event Report Form sent by overnight mail or courier service.
- Initial notification via telephone does not replace the need for the Investigator to complete and sign the Serious Adverse Event Report Form within the designated reporting time frames.
- Once the study has ended, serious event(s) suspected to be related to investigational product will be reported to Amgen if the Investigator becomes aware of a serious

18 May 2022 Page 44 of 69

adverse event. The Investigator should use the paper-based Serious Adverse Event Report Form to report the event.

18 May 2022 Page 45 of 69

Figure 2: Sample Serious Adverse Event Report Form

18 May 2022 Page 46 of 69

A	Clinic	cal Trial S	erious	s Adv	erse l	Εv	ent	Rep	ort	t —	Pha	15	e 1–	4	\top				
20220024		Notify .	Amgen V	Vithin 24	Hours of	kmo	wiedg	e of ti	he ei	vent						_			
Labcorp Study#																	Nev		
8493285																Ш	Foll	low-up	
Sotorasib																			
(AMG 510)															\perp				
		·	. 770																
1. SITE INFORMAT		(Sponsor) Safe	ety US:	Email:	[name]	or	ax.	[name]				
5ite Number	1014	In	vestigator							Co	untry			Т		-	Date	of Report	
															Di	ау	M	onth Ye	ar
	Reporter			Phone N	lumber						Т	Fax	Numbe	r					
				()							()					
2. SUBJECT INFO	RMATION																		
Subject ID		Age at eve	ent onset					Se	x			Ra	ce					, provide End o	of .
								[□F		и				50	tudy d	late		
3. SERIOUS ADVE														se E	ver	nt S	umi	mary CRF	'
Provide the date the In Serious Adverse Event Diag			Serious	Adverse	Event Info	orma	tion:	Day	M	lonth	—	ear F	Velationship	_				Outcome	Check
If diagnosis is unknow	n, enter Signs /						only if event	Serious Criteria				onat	de possib	ility th				of Event	anly if event is
Symptom When Final Diagnosis is	known, enter as						oc- curred	code	mey	nave o			by IP or ninister th			evice		01 Resolved	related to
Adverse Ev	ent	Date Star	ted	Da	ite Ended		before first	(see			If	yes:	see secti	on 10)			02 Nat resolved 03 Fetel	study proce-
List one event per line. If eve							dase of	codes below)	١.			.		l			04 Unknown		dure eg.
Cause of Death. Entry of "Dea as this is an ou		vie,					IF.	,	Sat	orazio	⊈Pidevio	•> *	*Pidevice>	4P6	evice>	<pli>de√</pli>	/ice>		biopsy
		Day Month	Year	Day	Month Ye	ar			No-7	15/	No-4 YE	٠,	64 YS4	No/	Y5/	No-	Y5/		
									H	Н	+	+				H			
									П	П	7	\top	_			Г			
									Ц	Ц	4	4	\bot						
												1							
Serious 01 Fatal		03 Required	d hospitali	ization		05 F	Persiste	ent or s	signif	ficant	disa	oility	y /inca;	pacit	y	0	7 Ot	her medical	y
Criteria: 02 Immediate		ning 04 Prolonge	ed hospita	alization		06 C	Congen	nital an	oma	ly/b	irth d	efec	at			in	npor	tant serious	event
4. HOSPITALIZATI	ON	,,,,,,,,,,,,,,,,,,,,,,,,,,,,,,,,,,,,,,,	,,,,,,,,,	,,,,,,,,	,,,,,,,,,,,	_		D-4		- 144 -	_					D-4	Dia	-1	
							Da		Mont Mont	mitte th	y Yea	г			Day		Mor	charged nth Year	
Was subject hospit	_	•		_	to this										_				
		If yes, please cor	mplete da	te(s):											_	_			
5. INVESTIGATION	IAL PRODUC	Initial Start Date	_		Prior to, o	r at f	ime of F	event				Δr	ction Ta	ken v	with f	Produ	ıct	Lot#and Ser	ial ff
			Date	of Dose	Dose		_	toute	Т	Frequ	өпсу	٦.	l Still bei						
		Day Month		Month								02	Perma	nently					
		Year	Y	ear	 		\vdash		+			03	Withhe	ld			+		
																		Lot#Unknown	
Sotorasib Blinded Dop	en Label																	Seriel#	-
												T						Lot# Unknown	
												ı						Serial #	_
< <ip device="">> Blinded</ip>	Open Label											+					-	Unizown	
																		Lot#Unknown	
< <ip device="">></ip>	□Open Label																	Seriel# Unknown	-
, January 1												T						Lot #	
																		Serial	
< <ip device="">> Blinded</ip>		rial SAF Report	Direct	4 4 1/2/	0.0 Effe	Sister .	data 2	22 /	al 20	40		CAI	FR Cre	at-	6.00	8.54		Unizoun	
FL/PDM-0115	mark Later History Fr	CAME AND PERSONS IN		1 TALL NO. 1 E.	a see a "Friend"	WINDS A	AMERICAN A	-3-9E/F	40- F18	1000		-100	THE RESERVE	well bear.	4 875	- F100 (F4) P	15-58	100	

18 May 2022 Page 47 of 69

Page 1 of 3

2022 Labcorp 8493 Sotos (AMG	Notify Amgen Within 24 Hours of knowledge of the event Study# (285 rasib (510)												w-up				
Site Number Subject ID Number																	
	OMITANT	MEDICATIO	NS (eq. cl	homotho	ranyl	Any Co	ncomitant	Modic	eations?	I I No.	п Уес	If you	place		nloto:		
	dication Nar		Start	Date	S	top Date	Co-su	spect	Cont	inuing		11 yes	Rou		Freq.		ent Med
			Dey Nor	th Year	Day	North Year	No-/	1664	No-/	Y88*						No-/	Yee-/
														\dashv			
														\Box			
7. RELE	VANT MED	ICAL HISTO	ORY (inclu	ude date	s, aller	gies and a	ny rele	ant p	nior th	erapy)						
8. RELE	VANT LAB	ORATORY	VALUES (include I	baselin	ne values)	Any Rel	evant l	Laborat	ory valu	ies? [□No□	□ Yes,	If ye	s, pleas	e comple	ite:
	Unit							+		_					-		+
Date Day N	Vonth Year				-			+		_					_		+
								\top		\top					\neg		
								T									
		NT TESTS	'diagnost	ics and p	roced	ures)	Алу (Other F	Relevan	t tests?		۰ - ۱	res, If	yes, p	please o	omplete:	
	Date Vonth Year			Additions	al Tests	5					Res	sults				Uni	ts
		1						\top							-+		
		+						+							\dashv		

FORM-015482 Clinical Trial SAE Report – Phase 1-4 V 10.0 Effective date: 23-April-2018 Page 2 of 3

SAER Created: 29-MAR-2022

18 May 2022 Page 48 of 69

A	Clinical Trial Serious Advers	e Event Report – Phase 1–4	
20220024	Notify Amgen Within 24 Hour	s of knowledge of the event	
Labcorp Study#			□New
8493285			□Follow-up
Sotorasib			
(AMG 510)			
(-			
	Site Number	Subject ID Number	
10. CASE DESCRI	PTION (Provide narrative details of events list	ted in section 3) For each event in section 3, w	here relationship=Yes.
please provide ratio		•	
Signature of Investigat	or or Designee	Title	Date
	report that the information on this form, including		
	y assessments, is being provided to Amgen by the ly, or by a Qualified Medical Person authorized by the		
Investigator for this stud			

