8.6. Safety and Tolerability Assessments

8.6.1. Adverse Events

All AEs will be coded using the Medical Dictionary for Regulatory Activities (MedDRA) Version 25.0. (or higher if a new version is issued during the study; see the DMP for more details).

A treatment-emergent adverse event (TEAE) will be defined as an AE that starts during or after the first dose, or starts prior to the first dose and increases in severity after the first dose.

A treatment related TEAE will be defined as a TEAE with a relationship of possibly related or related to the study treatment, as determined by the investigator.

All AEs will be listed. In addition to the data recorded in the database, the listings will include derived onset time and duration. Onset time will be calculated from the time of dosing for TEAEs only.

The frequency of subjects with TEAEs and the number of TEAEs will be summarized for the following categories:

- TEAEs (overall, serious, leading to discontinuation, and leading to death) by treatment
- TEAEs by severity and treatment
- Treatment-related TEAEs (overall, serious, leading to discontinuation, and leading to death) by treatment
- Treatment-related TEAEs by severity and treatment

The frequency of subjects will be summarized separately for TEAEs and treatment-related TEAEs by the following:

- System organ class, preferred term, severity and treatment
- Preferred term, severity and treatment

For the AE data the following rules will apply:

- For the derivation of TEAE status: If the start date/time of an AE is incomplete or missing, an AE will be assumed to be a TEAE, unless the incomplete start date/time or the end date/time indicates an AE started prior to the first dose.
- For the derivation of treatment-related TEAE status: If the study treatment relationship for a TEAE is missing, a TEAE will be assumed to be a treatment-related TEAE.

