- For the derivation of onset time (applicable to TEAEs only): If the start date/time of a TEAE is missing, onset time will not be calculated. If the start date/time of a TEAE is incomplete, where possible, the minimum possible onset time will be calculated and presented in '≥DD:HH:MM' format (eg, if the date/time of the last associated dose is 01MAY2019/08:00 and recorded start date/time of a TEAE is 03MAY2019, then the minimum possible onset time will be calculated by assuming a TEAE started at the first hour and minute of 03MAY2019 [03MAY2019/00:00], thus will be presented as onset time ≥01:16:00 in the listing). If the start date of a TEAE is the same as the date of the last associated dose but the start time of a TEAE is missing, an onset time will be presented as '≥00:00:01'. Any clock changes will be accounted for in the derivation.
- For the derivation of duration (applicable to all AEs): If the end date/time of an AE is missing, duration will not be calculated. If the start or end date/time of an AE is

incomplete, where possible, the maximum possible duration will be calculated and presented in ‘ \leq DD:HH:MM’ format (eg, if the start of an AE date/time is 01MAY2019/08:00 and its recorded end date/time is 03MAY2019, then the maximum possible duration will be calculated by assuming an AE ended at the last hour and minute of 03MAY2019 [03MAY2019/23:59], thus will be presented as duration \leq 02:15:59 in the listing). Any clock changes will be accounted for in the derivation.

- For the calculation of TEAE summary statistics: If the severity of a TEAE is missing, that TEAE will be counted under the ‘missing’ category.
- For the calculation of TEAE summary statistics: If a subject experienced multiple TEAEs with the same preferred term for the same treatment, this will be counted as 1 TEAE for that treatment under the maximum severity recorded.

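### An adverse event that worsens after the Day 9 combination is recorded once at its worst grade with no listed date for the change, so the severity-by-treatment tables show that grade under sotorasib alone

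*Protocol*

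**What the plan says.** **Recording.** Protocol Appendix 1 (Recording Adverse Events and Serious Adverse Events) tells the investigator that if severity "changes from the date of onset to the date of resolution, record as a single event with the worst severity". The attributes to be assigned include onset and resolution dates, whether the event began before the first dose, one severity and one relatedness assessment. A date of grade change is not among them. The follow-up part of the same appendix adds: "New or updated information will be recorded in the originally completed eCRF".

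**Design.** Subjects receive sotorasib on Day 1, omeprazole on Days 4 to 8, and omeprazole with sotorasib and cola on Day 9 (Protocol 3.1; SAP 4). Adverse events are collected continuously from the Day 1 dose to end of study on Day 11 (Protocol Appendix 8).

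**Reporting.** SAP 6, Table 1, gives two treatments for the tables: sotorasib alone and the combination. SAP 8.6.1 plans "TEAEs by severity and treatment", with a matching table for treatment-related events. Repeats of a preferred term within a treatment are collapsed: "this will be counted as 1 TEAE for that treatment under the maximum severity recorded". No sentence in the SAP says how an event is assigned to a treatment. The nearest hint is in the worked example for onset time in the listing: "if the date/time of the last associated dose is 01MAY2019/08:00".

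**The concern.** Each subject passes through the treatments in a fixed order, so one continuing event can belong to more than one treatment. Keeping one record at the worst grade is a normal convention when a subject has one treatment. Here the severity tables are split by treatment, and the record does not show which treatment preceded the worst grade.

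The secondary objective is the safety and tolerability of the combination. Worsening after the Day 9 dose is part of what the tables should show, and it could appear against the reference treatment instead. Persisting complaints are conceivable: Protocol 1.4.1.2 names diarrhea, nausea, vomiting and abdominal pain for both sotorasib and omeprazole. It also names raised liver enzymes for sotorasib, and the only scheduled laboratory tests after dosing starts are on Day 8 and Day 11. A clinically significant rise found on Day 8 and higher on Day 11 would become one worst-grade event with onset before the combination.

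**Working it through.** The plan states no figure on this point, so there is nothing to reproduce. The check follows one event through Appendix 1 and SAP 8.6.1.

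**Inputs**
- Up to 14 enrolled and 12 completing (Protocol 3.1, SAP 4).
- Two treatment columns (SAP 6, Table 1).
- Listed dates: onset and resolution (Protocol Appendix 1).
- Assumed event, for illustration: Grade 1 from Day 2, unresolved, Grade 2 after the Day 9 dose.

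**Step 1: the record.** Appendix 1 gives one event, onset Day 2, severity Grade 2.

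**Step 2: the tables.** Two assignment rules can be applied with the listed attributes. A third needs the date of worsening.

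| Assignment rule | Sotorasib alone | Combination |
|---|---|---|
| By onset (last dose before onset) | Grade 2 | no event |
| Under every treatment in which the event was ongoing | Grade 2 | Grade 2 |
| By onset, plus dated worsening (not possible from the listed attributes) | Grade 1 | Grade 2 |

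The third row describes what happened. Under both feasible rules the sotorasib-alone cell is one grade too high. Under the onset rule the combination cell is also empty when it should hold a Grade 2 event.

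**Step 3: size.** One event moves one subject between cells.
- 1/14 = 0.071, or 7.1 percentage points.
- 1/12 = 0.083, or 8.3 percentage points.

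Under the onset rule, with 14 subjects, Grade 2 on sotorasib alone is 7.1 points too high, Grade 1 there is 7.1 points too low, and Grade 2 on the combination is 7.1 points too low.

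**Step 4: does another SAP rule correct this?** The worsening clause in the TEAE definition covers an event that "starts prior to the first dose and increases in severity after the first dose". It refers to the first dose of the study, not the first dose of each treatment, so it does not reach an event that starts on Day 2. The maximum-severity rule works within a treatment and does not separate grades between treatments.

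**The case against.** The strongest reply is that few events will be affected and that readers can see them. The event must last about a week after a single dose and then worsen. Protocol 1.2 gives a mean half-life of 5 hours, so Day 9 is 192/5, about 38 half-lives, after the Day 1 dose. An event that resolves and returns after Day 9 is a new record and is placed correctly. All adverse events are listed with onset time and duration, Protocol 8.4 allows subject-level data in place of tables when incidence is low, and SAP 8.6.6 plans no inference on safety. All of this stands and limits the weight of the point. The rule in Protocol 4.5 on withdrawal from dosing at Grade 3 or above helps less, because Day 9 is the last dose and an event can reach that grade afterwards.

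Splitting a continuing event into two records would also raise the number of TEAEs and give the first record an artificial end date. That stands too, and the fix allows for it.

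Several stronger readings are tempting, but the documents do not support them:
- **That the recording rule defeats the TEAE definition.** Protocol 7.2.1 sends most pre-dose events to medical history. Appendix 1 makes a worsened pre-existing condition an adverse event in its own right and records whether an event began before the first dose. At most, serious or procedure-related pre-dose events remain.
- **That the date of worsening is never collected.** The eCRF and its completion instructions are not in the documents. Subjects are resident and questioned at least daily, so source notes may hold the date. The documents show only that it is not a listed attribute.
- **That the error always favours the combination.** If events are counted under every treatment in which they are ongoing, an event at its worst after Day 1 and milder by Day 9 would overstate the combination.
- **That any event still ongoing at Day 4 or Day 9 is affected.** The event must also change grade, and worsening on omeprazole alone removes nothing from the combination column.

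**Conclusion.** The point holds in a narrow form. For an event that starts after the Day 1 dose, is ongoing at Day 9 and worsens after the Day 9 dose, the sotorasib-alone column carries a grade reached only after the combination. This is so whether events are assigned by onset or counted under every treatment in which they were ongoing. Loss of the event from the combination column follows only under assignment by onset, which the SAP's reference to a last associated dose implies but does not state.

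Each such event is worth 7.1 percentage points of 14 subjects or 8.3 of 12. The documents give no frequency, and the number is probably small. The conclusion assumes that the eCRF captures no more than the attributes listed in Appendix 1. If it already dates grade changes, only the missing SAP rule remains. The effect is on a secondary, descriptive table, but that table serves the stated safety objective and the correction is cheap, so the change is worth making.

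**What to change.** **Protocol Appendix 1 and the eCRF completion instructions.** Keep one record per event. Add the date and grade of each severity increase that follows the first dose of a later treatment. As an alternative, open a linked record at the worsening, counted once in the overall number of TEAEs and keeping the true overall duration.

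**SAP 8.6.1.** State that each TEAE is assigned to the last treatment given before its onset. State also that an ongoing event which worsens after a later treatment is counted under that treatment at the worsened grade, while the earlier treatment keeps the grade reached before it. The same text should say where events starting on omeprazole alone (Days 4 to 8) are shown, since Table 1 has no column for them.

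**Cost.** A few extra eCRF entries and one derivation rule. A repeated preferred term already counts once per treatment at maximum severity, so the change does not double-count within a column.
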